8.2. Risk-benefit for subjects participating in the clinical investigation

The investigation is conducted in accordance with current law and applicable standards, see section 15, Statement of Compliance. The rights, safety and well-being of human subjects shall prevail over the interest of science of society.

Risks in this investigation are considered equal to the use of other wound care products on the marked (with silver). Risks associated with the use of wound care products are skin irritation/inflammation, allergic skin reaction, maceration, pain, hyper-granulation, and blistering. See section 18, Adverse Events and Adverse Device Effects for details.

There is no known interaction between the use of the test product and the medication participants can take – except from what is stated in the exclusion criterions. Disadvantages of testing (trial engagement) may be the time spent on visits and transport.

The overall clinically benefits of Biatain Fiber Ag may include, to be investigated in the study; moist wound healing,

Adequately exudate management provides a moist wound healing environment and together with sufficient antimicrobial effect this will pave the way for healing of wounds with delayed healing due to bacteria or wounds at risk of infection.

8.3. Risk Analysis for the conduct of the clinical investigation

A risk assessment of the clinical investigation will be conducted initially prior to the first subject enrolment and periodically re-assessed based on any new risks identified through the process. This assessment will be completed throughout the duration of the investigation, as defined by the study team. A risk-based monitoring strategy may be implemented including on-site remote, and central monitoring. Details of the strategy are defined in the monitoring plan in section 9.

8.4. Delegation of responsibility

Before initiation of the clinical investigation, sponsor must be provided with key personnel signed and dated curriculum vitae (not more than 2 years old) to verify their qualifications. Key site personnel are those, who treat or evaluate subject data in the clinical investigation. Also, the sponsor will ensure that all site personnel are trained in the investigation procedures, how to complete the CRFs, procedure for reporting an adverse event or serious adverse event (how, when, to whom), and who to contact in case of emergency related to the investigational device.

9. Monitoring Plan

The sponsor is responsible for ensuring appropriate monitoring of the clinical investigation activities as described below.

The monitors will be the primary contact for the principal investigator and clinical investigation site personnel.

Monitoring activities are mandatory as per good clinical practice, however the extend and depth of these activities depend on the criticality of the clinical investigation, speed of enrolment, the experience of the clinical investigation site personnel in carrying out clinical investigations and specific study designs.

For the purpose of this clinical investigation the below described monitoring procedures have been determined.

9.1. Site selection visit

Depending on the prospective clinical investigation sites experience with the specific investigational device, an on-site qualification or site selection visit shall be performed during which the feasibility of the clinical investigation requirements will be discussed and common agreement between sponsor and principal investigator shall be reached. This visit may also be replaced by one or more phone calls or conducted remotely, using Microsoft Teams.

9.2. Initiation visit

All clinical investigation sites will complete an initiation visit with full training on all aspects of the clinical investigation. The initiation visit can be held as a physical meeting or remotely, using Microsoft Teams, Skype or Face Time. Initiation visit will be held as close to study start as possible.

9.3. Monitoring visit(s)

The site dedicated monitor is to ensure adherence to the clinical investigation plan, accurate data recording on the e-CRFs and to monitor recruitment rates and adherence to follow-up schedules. The principal investigator shall permit and assist the monitor to carry out verification of completed e-CRFs against data in the source documents.

The principal investigator can delegate tasks to his/her collaborators, however the roles and responsibilities as time period of involvement for each clinical site personnel must be documented on the Site Personnel signature and delegation list as well as training received before getting involved with the clinical investigation must be documented in the Clinical investigation training log.

The monitor shall inform the sponsor about any problems relating to facilities, technical equipment or medical staff at the clinical investigation site. During the clinical investigation, monitors shall check that appropriate written informed consents have been obtained. The monitor shall also be responsible for notifying such deficiencies in writing to the principal investigator and convene with the clinical investigation site personnel appropriate and timely corrective actions.

The sponsor, or delegate, will provide clinical monitoring, including review of eCRF with verification to the source documentation, as defined in the monitoring plan.

The monitor shall make written reports to the sponsor, after each visit and provide written action items if any, to the principal investigator or clinical investigation site personnel.

All data collected can be directly entered into the eCRF and the EDC system will via edit checks ensure that all fields are completed in the eCRF. Monitor will ensure by 100% monitoring, that all queries are timely resolved.

Source data verification will be performed to the extent it is possible. The Source Data Specification Form must be completed at the initiation visit detailing the location of the source data for each data point. Where no source data (besides the eCRF) is available the contents of the eCRF will be monitored.

The Informed Consent Forms and AE/ADE will be 100% monitored for timely completeness.

Only the investigator, delegated site personnel and the sponsor representatives will have access to all the eCRFs.

9.4. Source data verification

A source document is a document in which data collected for a clinical trial is first recorded. This data is usually later entered in the electronic case report form (eCRF).

Source documents are defined as "original documents, data, and records. Source documents contain source data, which is defined as all information in original records and certified copies of original records of clinical findings, observations, or other activities in a clinical trial necessary for the reconstruction and evaluation of the trial.

All documents and data related to the clinical investigation handled by site personnel, shall be produced and maintained in a way that assures reliability, integrity, control and traceability, and shall be appropriately stored to provide a complete history.

The Principal Investigator shall assure the accuracy, attribution, completeness, legibility and timeliness of the data reported to the sponsor in the eCRFs and in all required reports. All printed copies of electronic source documents shall be certified, as indicated by a dated signature by the investigational site personnel at the time the document is printed. Special requirements should be applied to the capture, review and retention of electronic source data, to ensure reliability, quality, integrity and traceability.

The data reported in the eCRFs shall be derived from source documents and be consistent with these source documents, and any discrepancies shall be explained in writing. In some cases, the eCRF can serve as the source document and this must be documented on the Source Data Specification Form. The Source Data Specification Form must be completed at the initiation visit detailing the location of the source data for each data point.

10. Statistical considerations

10.1. Definition of analysis populations

Intention to Treat (ITT) and Safety populations will be defined at a formal data review meeting before database lock. As a minimum, the data manager, the clinical manager, and the statistician will be involved in the classification of subjects.

The Safety population will constitute by subjects who have given informed consent. Due to the design, the ITT population is identical to the safety population.

The full analysis set (FAS) will be constituted by all subjects with valid informed consent who have been exposed to the Test Product, with information on at least either primary or secondary endpoints.

All statistical analysis will be based upon the FAS population whereas adverse events and Device deficiencies will be assessed based on the safety/ITT population. Invalid individual data points may be omitted from analysis even though the corresponding subject is part of the FAS population. Any exclusion of data points will be documented.

A formal per protocol (PP) population will be performed for the primary, secondary and exploratory endpoints. Considering the data obtained it might also be considered to make additional explorative analyses based on a subset of the ITT population.

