6.5. Screening failure

Subjects that have signed the Informed Consent Form but fails to comply with inclusion or exclusion criteria are considered screening failures. A screening failure can be replaced by a new subject if the subject can complete the investigation within timelines (before last subject last visit and within visit windows).

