6.6. Point of enrolment

A subject is considered enrolled in the investigation when the written informed consent is obtained. The expected duration for each subject is described in section 5.1.

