10.2. Analysis of endpoints, individual questions, and assessments

All collected data including withdrawals will be accounted for in listings. All endpoints and baseline information will be listed and summarized by descriptive statistics. The summaries will be done in total and by the different population groups. Summaries and listing will include both safety/ITT and FAS population.

Summary statistics for continuous variables are presented with N, Mean, SD (standard deviation), Median, Min and Max, where N denotes the number of subjects contributing with non-missing data. For discrete variables, summary statistics are presented with N and percentage, where percentage is based on the total number of subjects/observations with non-missing data.

Other summaries and analyses can be made, if relevant.

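### The Safety set is defined by consent with no exposure condition, so consented subjects who are never dressed would dilute the adverse-device-effect percentages

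*Combined protocol and SAP*

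**What the plan says.** Section 10.1 of the protocol defines the set for safety reporting by consent alone: "The Safety population will constitute by subjects who have given informed consent". It adds "Due to the design, the ITT population is identical to the safety population", and states that "adverse events and Device deficiencies will be assessed based on the safety/ITT population".

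Exposure is a condition only for the full analysis set (FAS). That set takes consented subjects "who have been exposed to the Test Product, with information on at least either primary or secondary endpoints".

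Section 6.6 fixes enrolment at signature: "A subject is considered enrolled in the investigation when the written informed consent is obtained". Section 6.5 then describes a group who have signed but should not continue: "Subjects that have signed the Informed Consent Form but fails to comply with inclusion or exclusion criteria are considered screening failures". It also provides that "A screening failure can be replaced by a new subject if the subject can complete the investigation within timelines".

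Three provisions bear on how the definition would work in practice:
- Section 10.1 has the ITT and Safety populations settled at a data review meeting before database lock.
- Section 10.2 says that, for discrete variables, "percentage is based on the total number of subjects/observations with non-missing data".
- Section 10.2 also says that summaries and listings will cover both the safety/ITT and the FAS populations.

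**The concern.** An adverse device effect is an adverse event related to use of the dressing (section 18.2). A subject who signed consent but was never dressed is not at risk of one. Counting that subject adds to the denominator and leaves the numerator unchanged, so the reported percentage falls below the rate among subjects who used the product.

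The direction matters because the study has one arm, and no concurrent control group carries the same dilution. Section 2 says the data will be compared with data on similar devices to establish a similar safety profile. Table 4 in section 18.2 lists expected device-effect rates of 1% to 10%, taken from studies of other silver products. A denominator containing unexposed subjects moves the observed figure in the device's favour in any such comparison.

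The plan applies an exposure condition to the set used for efficacy but not to the set that carries device safety.

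**Working it through.** **Can an unexposed subject be in the Safety set?** Sections 10.1, 6.5, 6.6 and 7.1 are read together.
1. The only stated criterion for Safety is consent (10.1).
2. Consent is the point of enrolment (6.6). In the V1 list of section 7.1, signature comes before dressing application.
3. Screening failures are by definition people who have signed (6.5).
4. No section removes screening failures or never-dressed subjects from Safety.

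Such a subject therefore belongs to the Safety set as written.

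**Is another planned set free of the problem?** The FAS requires exposure but also endpoint information, so it is not by definition the set of all exposed subjects. How far it would differ cannot be determined: withdrawn subjects are encouraged to attend V3 (5.1), and some assessments are redacted.

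**Size.** The plan gives no figure for the Safety denominator and no count of consented, undressed subjects, so there is nothing to reproduce. The inputs are:
- 50 exposed subjects: an assumption, set at the planned enrolment (10.4)
- 5 subjects with an adverse device effect: an assumption, giving 10%, the highest rate in Table 4
- s consented but undressed subjects: an assumption, shown over a range

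Reported percentage = 5/(50 + s). Relative reduction = s/(50 + s). Intervals are exact (Clopper-Pearson) 95%.

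| s | Reported | 95% CI | Relative reduction |
|---|---|---|---|
| 0 | 5/50 = 10.0% | 3.3 to 21.8 | 0 |
| 1 | 5/51 = 9.8% | 3.3 to 21.4 | 1/51 = 2.0% |
| 2 | 5/52 = 9.6% | 3.2 to 21.0 | 2/52 = 3.8% |
| 5 | 5/55 = 9.1% | 3.0 to 20.0 | 5/55 = 9.1% |

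This layout assumes that screening failures are replaced, as 6.5 allows. If they are not, and 50 is the number consented, a true 10% rate is reported as 10% × (50 − s)/50. That gives 9.8%, 9.6% and 9.0% for s = 1, 2 and 5, which is almost the same.

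The absolute shift in the table is 0.2 to 0.9 percentage points, against an interval running from about 3% to 22%.

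**The case against.** The strongest reply is that the plan already has the means to deal with this and that little depends on it.

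- **Dual summaries (10.2).** If the statement that summaries include both safety/ITT and FAS covers safety data, a percentage on exposed subjects is already planned. Its reach is unclear. The paragraph concerns endpoints and baseline information, and 10.1 specifically places adverse events on safety/ITT. This softens the point without settling it, because the FAS also requires endpoint information.
- **Data review meeting (10.1).** A never-dressed subject could be handled there. However, the only written Safety criterion is consent, so removing that subject would depart from the definition when the open-label data are already known.
- **Non-missing denominators (10.2).** This is not an exposure rule. Nothing says that an undressed subject's event status counts as missing.
- **Few subjects affected.** This stands. Eligibility is reviewed at V0 and again at V1, where the check is listed before signature and the dressing is applied at the same visit (7.1).
- **No decision depends on it.** This also stands. Table 4 sets no acceptance limit, and 10.5 plans no test beyond the primary one.

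A reader might infer that every device-related percentage, device deficiencies included, can only be lowered. The documents do not support that. Section 18.3 counts use errors and labelling inadequacies as deficiencies, and these can arise before a dressing is applied. An undressed subject could therefore add to the deficiency numerator as well. For the same reason, an exposed-only denominator would be wrong for deficiencies, because it could drop those found before application from the table.

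**Conclusion.** The point holds for adverse-device-effect percentages. Under 10.1 as written, consented subjects who are never dressed enter the denominator and can only lower those percentages. None of the three limiting provisions states an exposure rule.

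The size is nil if every consented subject is dressed. In the assumed example, 1 to 5 undressed subjects lower a 10.0% rate by 0.2 to 0.9 percentage points, which is small beside the sampling uncertainty. The example rests on assumed counts throughout.

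Event counts are unaffected, as is the primary analysis, which uses the FAS. A reader might infer that the study's safety conclusion is compromised. The documents do not support that: no safety test or acceptance limit uses the percentage, and a consent-based set is suitable for listing all events. This is a low-priority wording correction.

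**What to change.** Amend section 10.1 before database lock:
1. Define the Safety set as all consented subjects exposed to at least one test dressing, with or without endpoint data. Use it as the denominator for adverse-event and adverse-device-effect percentages.
2. Keep all consented subjects as a separate set. Use it for disposition, for listing events before or without exposure, and for reporting all device deficiencies, including those found before application.
3. State that screening failures who were never dressed belong only to the second set.
4. Amend the sentence equating ITT with Safety, and bring the combined safety/ITT label in 10.1 and 10.2 into line, so that it is clear which set each safety summary uses.

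The cost is a small wording change. No extra subjects or data are needed, because exposure is already documented through dressing application at V1 (7.1) and the device accountability records (section 14). The one downside for the sponsor is slightly higher reported device-effect percentages if any consented subject was never dressed.

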5.9. Blinding

Not applicable

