10.3. Analysis of primary endpoint

The primary endpoint proportion of wounds healed will be analyzed using a binomial proportion test.

The purpose of the primary analysis is to show non-inferiority to the performance of the similar product Aquacel Ag (a silver containing gelling fiber) on proportion of wounds healed, 77 %, with a non-inferiority margin of 20 %. (1)

Since the performance of Aquacel Ag is a fixed proportion, this is equivalent to testing whether the performance of Biatain Fiber Ag is superior to $77 - 20 = 57$ %.

Let the null hypothesis and the alternative hypothesis be defined as:

- $H_0: \mu_{\text{Biatain Fiber Ag}} \leq 57$ % wounds healed
- $H_1: \mu_{\text{Biatain Fiber Ag}} > 57$ % wounds healed

Where Non-inferiority will be demonstrated if H_0 is rejected.

This will be done using the proc freq procedure with a binomial test and if the lower limit of the 95 % confidence interval is above 57 % H_0 is rejected, and the success criteria fulfilled.

Furthermore, as a conservative estimate, a sensitivity analysis will be performed on the primary endpoint, where patients lost to follow-up, or otherwise missing information, will be considered not healed in regards to their wound.

The exploratory endpoints will be analysed descriptively and presented with confidence intervals.

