10.4. Sample size

The primary endpoint is proportion of wounds healed and the sample size calculation is based on a proportion of 77 %. The design is a non-inferiority design, where we want to show noninferiority with a margin of 20 %.

This gives

The POWER Procedure
Z Noninferiority Test for Binomial Proportion

Fixed Scenario Elements	
Method	Normal approximation
Number of Sides	U
Null Proportion	0.77
Margin	-0.2
Alpha	0.025
Binomial Proportion	0.77
Nominal Power	0.8
Variance Estimate	Null Variance

Computed N Total	
Actual Power	N Total
0.801	44

Meaning a total of 44 completers gives a sufficient (80%) power. Accounting for dropouts (10%) gives us 50 subjects.

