10.5. Level of significance and power

The study is designed with a power of 80 % and testing of the primary analysis will be done using a one-sided 0.025 significance level. No other statistical test as pre-planned.

11. Data management

Data management and the final statistical analyses of all measurements described in this protocol are carried out by Clinical Strategies, Coloplast A/S.

Data will be collected through an electronic data capturing (EDC) system on electronic Case Report Form (eCRF), a secure, internet-based case report form. This system will be used to record all subject information collected in the investigation for secure data tracking and centralised data monitoring ("remote monitoring") done by monitors, as defined in the monitoring section.

The system is designed to be compliant with the FDA requirements of 21 CFR part 11. It is a validated data management system allowing only qualified and trained personnel to enter the system. The system has full audit trail and electronic signature.

The data management system has restricted role-based access control. The principal investigator or delegate must be trained in the system prior to getting access. The sponsor will be responsible for training the investigator or delegate, in completion of the eCRF. The training is web-based and must be completed before access to the investigation is granted. Training will be documented in the data management system. The data manager will also demonstrate the system on a virtual meeting. Only the principal investigator, or delegate, will be authorised to enter data in the eCRF.

The monitor, using his/her personal login information shall verify all critical data points against the source documents and issue electronic queries for the authorised clinical site personnel to respond, as defined in the monitoring section.

A critical quality control will be performed by the sponsor's data management team and queries issued where needed. Such queries must be resolved by the site personnel.

The principal investigator, using his/her personal login information, shall sign each eCRF.

Automated, real-time access to the data enable control on study compliance and safety assessments.

A full audit trail ensures, that each user's (site personnel, monitor, sponsor, data manager) access to and actions in the system is tracked.

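### Section 10.1 lets a recorded healing result be omitted as invalid from the primary analysis, in an open single-arm trial where two omitted unhealed results can change failure into success

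*Combined protocol and SAP*

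**What the plan says.** Section 10.1 bases all statistical analysis, and so the primary analysis, on the FAS. It then adds: "Invalid individual data points may be omitted from analysis even though the corresponding subject is part of the FAS population". Exclusions are to be documented. Invalid is not defined, no decision-maker or time is named for omitting a data point, and the primary endpoint is not set apart.

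The same section says: "Intention to Treat (ITT) and Safety populations will be defined at a formal data review meeting before database lock". At least the data manager, the clinical manager and the statistician take part in classifying subjects. Section 11 states that data management and the final analyses are "carried out by Clinical Strategies, Coloplast A/S", and section 6.3 identifies the clinical manager as sponsor staff. Section 5.1 describes a one-armed, open-label study, and the whole entry on blinding (5.9) is "Not applicable".

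Section 10.2 computes percentages from non-missing data. Section 10.3 declares success if the lower 95% limit for the healed proportion is above 57%, without naming the type of interval. It adds a sensitivity analysis in which patients lost to follow-up or with other missing information count as not healed. Section 10.5 says "testing of the primary analysis will be done using a one-sided 0.025 significance level".

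**The concern.** In a blinded two-arm trial, a review of data validity before lock is protected because the reviewers do not know which decision favours which arm. A single open arm tested against a constant has no such protection: anyone who sees the healed count knows whether the trial succeeds. A rule that lets a recorded outcome be set aside as invalid, with no definition and no exemption for the primary endpoint, is therefore a discretion exercised with the result in view.

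The direction of the effect is also fixed. An omitted unhealed result leaves the denominator only, so the estimate can only rise. The one-sided 0.025 level then holds only if omissions are unrelated to outcome, and the text does not require that. With about 50 subjects, each result carries enough weight to matter. The trial is meant to support a CE mark.

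**Working it through.** **Inputs.** Power: "The study is designed with a power of 80"% (10.5). Assumed rate: "the sample size calculation is based on a proportion of 77"% (10.4). Margin: "with a non-inferiority margin of 20"% (10.3), so the null is 0.77 − 0.20 = 0.57. One-sided alpha 0.025 (10.5). Completers 44, enrolled 50 (10.4).

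**The plan's own figure.** For a one-sample z test with null variance, n = [1.960·√(0.57·0.43) + 0.842·√(0.77·0.23)]² / 0.20² = (0.970 + 0.354)² / 0.04 = 43.9, so 44. Power at 44 is 0.801, as stated. Allowing for 10% dropout, 44/0.9 = 48.9, so 49; the plan enrols 50. The design figures reproduce.

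**Effect of omission.** For x healed among n, removing k unhealed results changes x/n to x/(n − k). Since 10.3 leaves the interval open, lower two-sided 95% limits are given for three types. Success needs more than 57%.

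| Result | Exact (Clopper-Pearson) | Wilson | Wald |
|---|---|---|---|
| 35/50 | 55.4% fails | 56.3% fails | 57.3% succeeds |
| 35/49 | 56.7% fails | 57.6% succeeds | 58.8% succeeds |
| 35/48 | 58.2% succeeds | 59.0% succeeds | 60.4% succeeds |
| 34/50 | 53.3% fails | 54.2% fails | 55.1% fails |
| 34/48 | 55.9% fails | 56.8% fails | 58.0% succeeds |
| 34/47 | 57.4% succeeds | 58.2% succeeds | 59.6% succeeds |

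At the 44 planned completers with exact limits, 31/44 fails (54.8%) and 31/42 succeeds (58.0%); 30/44 fails (52.4%) and 30/41 succeeds (57.1%).

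**Worst-case type I error.** Suppose that up to k unhealed results are removed whenever this produces success. Let c(k) be the smallest healed count, out of the original n, that then succeeds. The type I error is P(X ≥ c(k)) for X binomial with n and 0.57. With exact limits:

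| n | k = 0 | up to 2 | up to 3 |
|---|---|---|---|
| 50 | c = 36: 2.1% | c = 35: 4.2% | c = 34: 7.5% |
| 44 | c = 32: 2.3% | c = 31: 4.8% | c = 30: 8.8% |

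At n = 50, Wilson limits give the same three figures, and a single removal already reaches 4.2%. Wald limits start at 4.2% with no removal and rise to 7.5% (up to two) and 12.6% (up to three).

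**How often a trial would fall in this zone.** At the planned rate of 77% with exact limits, P(success) at n = 50 is 84.4% with no removals and 94.9% with up to three. The difference, about 11%, is the chance of a failed result that three omissions could reverse. At n = 44 it is 93.7% − 80.6% = 13%.

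**With omitted results kept as not healed.** The denominator stays at n, so 35/50 and 34/50 remain failures with exact limits and the type I error at n = 50 stays at 2.1%.

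**The case against.** The plan has real safeguards. Exclusions are documented (10.1) and all collected data are listed (10.2). Critical data points are checked against source, the investigator signs each eCRF, and there is a full audit trail (section 11). A Data Validation Plan, not seen here, sets consistency checks and may bear on what counts as invalid. The sensitivity analysis in 10.3, on its natural reading, would restore an omitted result as not healed and so reveal the change. All of this stands as protection against a hidden change. It does not close the gap: success rests on the primary lower limit alone, and 10.3 does not say that a recorded value later set aside counts as missing information.

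The error rates above also assume that only unhealed results are removed, and only when that helps. They bound what the rule permits; they do not estimate the effect of ordinary data cleaning. Reversals occur only just below the threshold.

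Three stronger readings are tempting, and the documents do not support them:

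- A reader might infer that the pre-lock meeting decides which data points to omit. Section 10.1 ties that meeting to populations and the classification of subjects, and says neither when nor by whom a data point is judged invalid.
- A reader might infer that classifying subjects can itself alter the primary result. Safety/ITT membership rests on consent. FAS membership rests on consent, exposure and having some endpoint information. None of these depends on whether the wound healed.
- A reader might infer that the plan leaves such a change undetectable, or that someone intends one. The safeguards above contradict the first, and nothing in the documents suggests the second.

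**Conclusion.** The point holds in limited form and is a cheap improvement worth making. The omission rule in 10.1 reaches the primary endpoint, uses an undefined term, and operates where healing status is visible and the threshold is fixed. With exact limits, two omitted unhealed results turn 35/50 from failure into success, and three do so for 34/50. The worst-case type I error at 50 subjects is 4.2% or 7.5%, against 2.1% without omission and a planned 2.5%.

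These figures assume 50 analysed subjects, exact limits, and deliberate omission of unhealed results only. The number of omissions needed depends on the interval type, but a route from failure to success exists under all three types examined.

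**What to change.** In 10.1 and 10.3, state that a recorded yes/no value for wound healed in a FAS subject is not omitted from the primary analysis. Errors are corrected by site query before database lock, a process section 11 already provides. Any value still judged invalid at lock counts as not healed in the primary analysis. Exclusions of such values are used only in the per-protocol analysis.

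The cost is a few sentences. The downside is that the primary estimate may be slightly conservative if a healed wound has an entry that cannot be resolved.

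Masking healing status in the review listings would not be a good substitute. Section 7.4 and Table 3 send healed subjects to a separate termination visit with different assessments, so the visit type alone reveals the outcome. Section 11 also describes real-time access to the data during the study.
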